**Purpose:**

To determine how frequently hypoglycemia occurs in older patients with diabetes, and determine if hypoglycemia adversely affects cardiac function in these patients.

**Hypothesis:**

Hypoglycemia can result in abnormalities in cardiac rhythm and autonomic function and can cause myocardial ischemia in elderly patients with diabetes.

**Objectives:**

1. To monitor blood sugar and cardiac function continuously for 6 days.
2. To determine if there is a correlation between hypoglycemia and alterations in cardiac rhythm, alterations in cardiovascular autonomic function and myocardial ischemia.
3. To collect baseline data to design a subsequent study to assess the effects of various interventions designed to protect the cardiovascular system against hypoglycemia if objectives 1 and 2 are achieved.

**Background:**

A variety of studies have shown that the risk of severe or fatal hypoglycemia associated with the use of insulin or oral agents increases exponentially with age ([name]). Hypoglycemia due to these agents is the commonest reason for iatrogenic hospitalization in the elderly (Budnitz). There are several reasons for this increased prevalence ([name]). The most important counter-regulatory hormone in the defense against hypoglycemia in normal subjects is glucagon, and the responses of this hormone to hypoglycemia are impaired in normal elderly subjects and, to an even greater extent, in elderly patients with diabetes. Many elderly patients have not been educated about the warning signs of hypoglycemia and, as a consequence, do not know how to interpret these symptoms when they occur. In addition, even when they are educated about them, elderly patients have reduced awareness of the autonomic warning symptoms of hypoglycemia (such as sweating, shakiness and a feeling of hunger). Finally, older patients have impaired psychomotor performance when their blood sugars are low, which prevents them from taking the appropriate steps to return their blood sugars to normal. Thus, the increased severity of hypoglycemia in the elderly is due to a variety of abnormalities, including decreased counter-regulatory hormone secretion, reduced knowledge and

awareness of warning symptoms, and altered psychomotor performance. Indeed, recent data suggest that asymptomatic hypoglycemia is shockingly common in these patients. When assessed by continuous glucose monitoring, 65% of elderly diabetic patients have frequent hypoglycemic episodes lasting up to an hour that are entirely asymptomatic (Munshi, [name]). The consequences of frequent, severe and/or asymptomatic hypoglycemia in this patient population have not been clearly defined. The risk of hospitalization and death is detailed above, but this is probably a "tip of the iceberg" phenomenon since hypoglycemia is so frequently asymptomatic in this age group. It is known that severe hypoglycemia increases the risk of dementia ([name]). Older patients on insulin have an increased frequency of falls and fractures, and this is more likely as the HgbA1C falls, implying that low blood sugars may be a contributing factor ([name]). Elderly patients with diabetes have an increased frequency of syncope, cardiac arrhythmias, myocardial infarction, and sudden death and the risk of these events is more than doubled in patients treated with agents that are known to cause hypoglycemia (Currie). However, other than some anecdotal reports of low blood sugars at the time of these events, no studies have carefully evaluated the relationship between hypoglycemia and cardiac function in this age group. In this study we propose to evaluate the association between hypoglycemia, as measured by continuous glucose monitoring, and cardiac rhythm, cardiovascular autonomic function and myocardial ischemia, as measured by continuous electrocardiographic (ECG) monitoring.

#### **Design, Specification of Endpoints, and Procedures:**

We propose a pilot study in 20 patients over age 70 who have had type 2 diabetes for at least 5 years and are being treated with insulin-glargine. All patients will have a BMI of between 20 and 35 Kg/M2, and an A1C between 7 and 8.5 %. All patients will have well controlled hypertension and hyperlipidemia. Patients with a GFR less than 40ml/min, poorly controlled CHF and active coronary artery disease or cerebrovascular disease will be excluded, although a past history of CAD or stroke will not result in exclusion. We will also exclude patients who are not fluent in English. These patients will be enrolled from the elderly diabetes clinic at Vancouver General Hospital. Patients will be contacted as per the information in the letter of initial contact. Briefly, appropriate patients will be sent a letter describing the study. At least one week later they will be contacted by a research nurse/research assistant who will explain the study, answer their questions, and if they agree to participate, will send them a copy of the consent for their perusal. If, after reading the consent, they are still interested in participating, they will be asked to come to the VGH Diabetes Centre of Gerontology Research Laboratory in the Research Pavilion at Vancouver General Hospital. At that time, a trained research nurse will instrument each patient with an iPro2 glucose sensor (Medtronic Canada). These sensors reliably and continuously measure blood glucose for periods of up to 7 days. Briefly, the skin will be swabbed with a disinfectant and a small catheter will be inserted subcutaneously. This catheter will be attached to a glucose sensor. Patients will

wear this sensor for 6 days. They will measure their glucose using a glucometer 4 times each day during this period and will also be given a log book to keep track of glucose values. They will also be asked to record any symptoms of hypoglycemia. At the end of 6 days the sensor will be removed.

At the same time the glucose sensor is started, a trained research nurse will connect the patient to an Icentia CardioSTAT, a continuous ambulatory ECG cardiac monitor. The Icentia CardioSTAT is a new heart monitor designed to record up to 7 days of continuous single-lead ECG in ambulatory conditions. The device has the shape of a thin, flexible strip of about 14cm x 3 cm to be applied on the subject's upper torso at the level of the second intercostals space. The CardioSTAT is held in place by means of 2 standard ECG gel electrodes (3M™ Red Dot™ 2560) allowing the skin to breathe freely underneath its' surface. A Hypafix dressing will be placed over the electrodes. The CardioSTAT is single-use. A new unit will be used for each subject.

Subjects will be asked to contact the study site if they are experiencing any discomfort, redness or irritation under the electrodes/Hypafix dressing. If needed, a clinic visit will be scheduled to assess and/or replace the electrodes/Hypafix dressing. At the end of the recording period the Cardio STAT will be returned to the manufacture for data download and proper disposal.

The CardioSTAT will not be used if the subject has 1) a chronic skin disorder on the upper torso; 2) an open wound, cut abrasion, burn or flaking skin at the application site; 3) known allergies to medical tape; or 4) presence of an active implantable device (such as a pacemaker, defibrillator, neurostimulator).

The archived ECG waveforms will be downloaded for QT and TWA analysis. The heart rate and QT interval will be measured at baseline and the end of each interval from the digitized ECG.

Patients and relevant family will be provided with in person and paper based education regarding the function and use of the monitor, implications for bathing and sleep, and contact information for troubleshooting. They will be asked to keep a log book of any cardiac symptoms during the 6 days of the study, as well as their activities. The iPro2 glucose and CardioSTAT monitors will undergo time synchronization to ensure ability to do correlative analysis.

This is a feasibility pilot to establish preliminary data for analysis. The CardioSTAT monitor will allow assessment of cardiac arrhythmias, myocardial ischemia and cardiovascular autonomic function. The results from the glucose sensor and the CardioSTAT monitor will be correlated and compared to each other to determine if hypoglycemia has an adverse effect on heart function. Hypoglycemia is likely to induce autonomic responses captured on the CardioSTAT and concordant ischemic ST changes if coronary disease is present. It may also detect any resultant arrhythmias, although ischemic arrhythmias are

uncommon in 6 days of monitoring. If we determine that hypoglycemia has negative effects on cardiac function, we may be able to design treatments that would prevent these effects from happening in the future.

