#### **Data Analysis:**

Autonomic function will be evaluated by assessing heart rate variability using autoregressive spectral analysis during hyperglycemia, euglycemia and hypoglycemia. Arrhythmia analysis will be performed using the standard algorithms that are normally used to assess data in the Holter laboratory, and will be correlated with prevailing blood sugar values. This will include standard diagnostic evaluation including mean, median and range of heart rate, quantitation of supraventricular and ventricular ectopy, and Tpeak-Tend. P wave duration and variability and T wave alternans will be measured as well and correlated with prevailing glucose values. ST segments to evaluate for ischemia will follow standard techniques in routine clinical software (GE Marquette, Wisconsin) that reports ST shifts during 5 minute epochs, and will be correlated with metrics of heart rate variability, absolute heart rate and symptoms.

Measurements will be performed by an experienced expert blinded to the patient's clinical status. QTc will be calculated using Bazett's formula (Bazett). The end of the T wave will be defined as the intersection of the maximum slope of the terminal T wave with the isoelectric TP segment. QT variability will be evaluated from digitized lead V2 at baseline. Each 5-minute epoch will be analyzed using a validated QT interval measurement algorithm proposed by Berger et al. (Berger), which computed mean QT, QT variance, mean heart rate, and heart rate variance. To measure beat-to-beat QT variability, a normalized QT variability index (QTVI) will be calculated. TWA will be measured from the digitized ECG using the spectral method as previously developed by the University Health Network Holter data site (Selvaraj). TWA magnitude ( $V_{alt}$ ) will be quantified over a 128-beat window which will be successively incremented by 16-beats until the end of each 5-minute epoch.

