#### **Statistical Analysis:**

Continuous variables will be expressed as mean and standard deviation or median and interquartile range (25th-75th percentiles) where appropriate. *Student's paired t test or the Wilcoxon signed rank test* and One-way repeated measures ANOVA or the Friedman test will be used for comparison as appropriate. The within-subject variance-covariance matrix will be evaluated by the compound symmetry method. Categorical variables will be presented as frequency or percentage. Fisher's exact test will be used for comparison at each glucose level. Cochran's Q test will be used for comparison of proportions. A two-tailed  $p$ -value  $<0.05$  will be considered statistically significant. Statistical analysis will be performed using SPSS (version 15.0.0, SPSS Inc.) and SAS version 8.2 (SAS Institute, Cary, NC).

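### Patients log their activities, but the analysis never uses those entries, so physical activity can mimic or mask a cardiac effect of hypoglycemia

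*Combined protocol and SAP*

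**What the plan says.** The Design section describes six days of simultaneous glucose and single-lead ECG recording while patients go about their daily lives. Of the patients it says: "They will be asked to keep a log book of any cardiac symptoms during the 6 days of the study, as well as their activities". Both monitors are time-synchronized. The glucose and ECG results "will be correlated and compared to each other to determine if hypoglycemia has an adverse effect on heart function".

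Data Analysis then states how each measure is handled:
- HRV: "Autonomic function will be evaluated by assessing heart rate variability using autoregressive spectral analysis during hyperglycemia, euglycemia and hypoglycemia".
- Arrhythmia analysis, which includes heart rate, ectopy and Tpeak-Tend: "will be correlated with prevailing blood sugar values".
- P wave measures and TWA: also correlated with prevailing glucose.
- ST shifts, reported in 5-minute epochs: "will be correlated with metrics of heart rate variability, absolute heart rate and symptoms".

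For two conditions, Statistical Analysis names "Student's paired t test or the Wilcoxon signed rank test". For more than two it names one-way repeated-measures ANOVA or the Friedman test, and for categorical data Fisher's exact test and Cochran's Q. No covariate, stratification, matching or restriction to rest is mentioned.

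**The concern.** Exertion can lower glucose in insulin-treated patients. It also raises heart rate, lowers HRV, adds ectopy and can shift the ST segment. This is general physiology and is not stated in the documents. Activity is therefore a possible common cause of the exposure and of most outcomes. The free-living design leaves it uncontrolled.

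If lows cluster with activity, low-glucose epochs will tend to show faster heart rates and lower HRV even when glucose does nothing to the heart. If lows cluster with rest or sleep, a real effect can be hidden. Either way the Design section would read the contrast as bearing on whether hypoglycemia harms heart function. Objective 3 would then carry it into the design of an intervention study.

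**Working it through.** The plan states no power, effect size or SD, so there is no figure of its own to reproduce. The check has two parts: where activity enters the analysis, and an illustration of what its absence could do.

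**1. Where activity enters**

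| Measure | Related to | Activity used? |
|---|---|---|
| HRV | three glucose states | no |
| Heart rate, ectopy, Tpeak-Tend | prevailing glucose | no |
| P wave, TWA | prevailing glucose | no |
| ST shift | HRV, heart rate, symptoms | no (symptoms are used) |

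**2. Why pairing does not help**

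Write a patient's mean heart rate in glucose state s as a + b × p(s). Here a is the patient's own level, b the rise in heart rate when active, and p(s) the share of epochs in that state spent active. With no true glucose effect, the paired difference is

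δ = b × [p(hypo) − p(eu)].

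The patient's level a cancels; the activity term does not.

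**3. Assumed inputs (none is in the documents)**

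- b = 20 bpm, range 10-30.
- Active share 15 percentage points higher in hypoglycemia than in euglycemia, range 10-20.
- Within-patient SD of the difference: 5-8 bpm.
- Patients with lows: 0.65 × 20 = 13. This borrows the 65% in Background, which describes patients with frequent asymptomatic episodes. The title of the study cited for it concerns poor glycemic control, whereas this trial requires A1C between 7 and 8.5%.

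Spurious difference: 0.15 × 20 = 3 bpm, with range 0.10 × 10 = 1 bpm to 0.20 × 30 = 6 bpm.

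**4. False-positive rate**

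Two-sided paired t test at 0.05, n = 13, 12 degrees of freedom, noncentrality λ = (δ / SD) × √13, with √13 = 3.606:

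| δ (bpm) | SD 8: λ, rejection | SD 5: λ, rejection |
|---|---|---|
| 0 | 0, 5% | 0, 5% |
| 1 | 0.45, 7% | 0.72, 10% |
| 3 | 1.35, 24% | 2.16, 51% |
| 6 | 2.70, 70% | 4.33, 98% |

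If all 20 patients had lows, the same δ of 1, 3 and 6 bpm would give 8-14%, 36-72% and 89-99.9%.

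**5. The other direction**

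If the active share is 15 points lower during lows, δ = −0.15 × 20 = −3 bpm. A true rise of 3 bpm would then appear as 3 − 3 = 0. Nothing in the documents fixes the sign.

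**The case against.** Several objections have force.

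- **The log is not wholly unused.** A reader might infer that no analysis touches it. Data Analysis does relate ST shifts to symptoms, so only the activity entries lack a stated use.
- **ST is a weaker case.** A reader might infer that a glucose-ST comparison is specified and confounded. Data Analysis lists none; that link comes only from Objective 2 and the general sentence in the Design section. Relating ST to absolute heart rate is also a partial handle on exertional change. It does not adjust a glucose-ST relation, and it cannot help heart rate or HRV, which are themselves outcomes.
- **The direction is unknown.** A low that follows a walk may fall at rest after heart rate has recovered, and nocturnal lows would bias the other way. The documents do not support a claim that the bias must create false positives.
- **It is a 20-patient feasibility pilot.** Background speaks of association and Objective 2 of correlation. This lowers the stakes, but the Design section still states its purpose in causal terms.
- **A remedy is imperfect.** Six days give 6 × 24 × 12 = 1,728 five-minute epochs per patient, or 34,560 for 20 patients. A handwritten log classifies them coarsely, and unlogged activity would be coded as rest. Activity may also respond to hypoglycemia, for example when a patient sits down, so adjustment is not guaranteed to be unbiased. This argues against making a rest-only analysis the sole or main one. It does not argue against reporting one.

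Blinding the ECG reader to clinical status guards against measurement bias, not against this.

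**Conclusion.** The omission is clear from the text: activities are logged, and no stated analysis uses them. HRV, heart rate, ectopy, Tpeak-Tend, P wave and TWA are related to glucose with unadjusted methods, and within-patient tests leave a time-varying confounder in place. The all-epoch results as planned cannot separate an effect of hypoglycemia from a difference in activity.

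The size is not known. The 7-98% range shows only that modest imbalances could matter, and it rests wholly on the assumed activity effect, activity shares, SD and number of patients with lows. A reader might take the central 24-51% as an estimate of the trial's error rate. The documents give no input that would support that, and they do not exclude an imbalance of zero or of the opposite sign. The study can run as designed, but its stated inference should not rest on the all-epoch comparison alone.

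**What to change.** 1. In the Design section, ask patients to record start and stop times for each logged activity.
2. In Data Analysis, flag each 5-minute epoch as active or at rest from that log, using a rule written before glucose and ECG data are combined.
3. Pre-specify a hypoglycemia-euglycemia comparison that takes account of activity, either with an epoch-level activity term in a model with patient as a random effect, or restricted to rest epochs using the paired tests already planned. Report it alongside the all-epoch result.
4. Claim an effect on heart function only if the two agree. Define agreement in advance by direction and approximate size, since the rest-only analysis will have fewer epochs. Otherwise describe the all-epoch finding as an unadjusted association.

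**Cost:** a small change to the log instructions, the work of coding the log, and a few sentences in the analysis plan. The 5-minute epochs and time synchronization already exist. The rest-only comparison loses some hypoglycemic epochs. Control stays partial because the log is self-reported and activity may itself respond to a low.

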#### **Data Analysis:**

Autonomic function will be evaluated by assessing heart rate variability using autoregressive spectral analysis during hyperglycemia, euglycemia and hypoglycemia. Arrhythmia analysis will be performed using the standard algorithms that are normally used to assess data in the Holter laboratory, and will be correlated with prevailing blood sugar values. This will include standard diagnostic evaluation including mean, median and range of heart rate, quantitation of supraventricular and ventricular ectopy, and Tpeak-Tend. P wave duration and variability and T wave alternans will be measured as well and correlated with prevailing glucose values. ST segments to evaluate for ischemia will follow standard techniques in routine clinical software (GE Marquette, Wisconsin) that reports ST shifts during 5 minute epochs, and will be correlated with metrics of heart rate variability, absolute heart rate and symptoms.

Measurements will be performed by an experienced expert blinded to the patient's clinical status. QTc will be calculated using Bazett's formula (Bazett). The end of the T wave will be defined as the intersection of the maximum slope of the terminal T wave with the isoelectric TP segment. QT variability will be evaluated from digitized lead V2 at baseline. Each 5-minute epoch will be analyzed using a validated QT interval measurement algorithm proposed by Berger et al. (Berger), which computed mean QT, QT variance, mean heart rate, and heart rate variance. To measure beat-to-beat QT variability, a normalized QT variability index (QTVI) will be calculated. TWA will be measured from the digitized ECG using the spectral method as previously developed by the University Health Network Holter data site (Selvaraj). TWA magnitude ( $V_{alt}$ ) will be quantified over a 128-beat window which will be successively incremented by 16-beats until the end of each 5-minute epoch.

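### For arrhythmia, P wave measures and T wave alternans the plan states only correlation with prevailing glucose, which is a weak measure of the hypoglycemia effect that objective 2 asks about

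*Combined protocol and SAP*

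**What the plan says.** The question is about low glucose. Objective 2 is "To determine if there is a correlation between hypoglycemia and alterations in cardiac rhythm", together with autonomic function and ischemia. The Design section says that the sensor and ECG results will be "correlated and compared to each other to determine if hypoglycemia has an adverse effect on heart function".

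The Data Analysis section then gives instructions by outcome:

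- Heart rate variability: "assessing heart rate variability using autoregressive spectral analysis during hyperglycemia, euglycemia and hypoglycemia".
- Arrhythmia measures (heart rate summaries, ectopy, Tpeak-Tend): these "will be correlated with prevailing blood sugar values".
- P wave duration and variability, and alternans: "T wave alternans will be measured as well and correlated with prevailing glucose values".

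Nothing restricts the last two instructions to low values or adds a threshold, a spline or a glucose-state term. No correlation method is named.

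The Statistical Analysis section lists paired t or Wilcoxon tests, repeated measures ANOVA or Friedman, Cochran's Q, and Fisher's exact test at each glucose level. It does not define the levels, name the factor compared in the continuous tests, or say which outcomes each test serves.

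**The concern.** A correlation over all prevailing glucose values describes how the measure moves with glucose in general. Entry requires "an A1C between 7 and 8.5" percent, and the Background describes low episodes of up to an hour, so most of a six-day record should lie in the euglycemic or high range. Those readings would then dominate the coefficient, and the contrast that objective 2 needs would contribute little to it. A single coefficient also assumes one direction of effect across the range, whereas the plan treats hyperglycemia as a state of its own for heart rate variability.

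The result has a use. Under objective 3 the data feed the design of an intervention study if objectives 1 and 2 are achieved. A coefficient near zero could be read as no effect, and it gives no effect size in usable units for that later study.

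**Working it through.** The plan gives no effect size, power or expected correlation, so there is no figure of its own to reproduce.

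**Inputs from the documents.** The plan is for 20 patients ("We propose a pilot study in 20 patients over age 70") monitored for six days ("To monitor blood sugar and cardiac function continuously for 6 days"), with 5-minute epochs in Data Analysis. That gives 6 x 24 x 12 = 1,728 epochs per patient and 20 x 1,728 = 34,560 in all.

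**Assumptions not in the documents.** Non-hypoglycemic glucose is lognormal with mean 9.7 and SD 3.0 mmol/L, cut off below 3.9. Low values are uniform from 2.5 to 3.9 (mean 3.2). Cut-offs are 3.9 and 10 mmol/L. The share p of low epochs is 1%, 2%, 5% or 10%, which is about 17 to 173 epochs per patient. Low glucose raises the ECG measure by d = 1 SD. Optionally, the measure also rises by b SD per mmol/L above 10.

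**Formula with b = 0.** r = d x p(1-p) x (mean low - mean other) / (SD of glucose x SD of measure), where the SD of the measure is the square root of 1 + d^2 x p(1-p). The mean of the other readings after truncation is about 9.71.

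- p = 1%: 0.0099 x (3.2 - 9.71) / (3.04 x 1.005) = -0.02.
- p = 10%: 0.09 x (3.2 - 9.71) / (3.45 x 1.044) = -0.16.

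**Simulation** (about 1 million epochs per scenario, d = 1):

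| Low share | Glucose sum of squares from low epochs | r, b = 0 | b at which r = 0 | r, b = 0.05 | r, b = 0.10 | Low minus euglycemic, SD |
|---|---|---|---|---|---|---|
| 1% | 4.5% | -0.02 | 0.012 | +0.06 | +0.15 | 1.00 |
| 2% | 8.5% | -0.04 | 0.024 | +0.04 | +0.13 | 0.99 |
| 5% | 18% | -0.09 | 0.058 | -0.01 | +0.07 | 1.00 |
| 10% | 29% | -0.16 | 0.11 | -0.09 | -0.01 | 1.00 |

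So 71% to 95% of the variation in glucose that drives r comes from readings that are not low. With d = 0.5 and b = 0, r runs from -0.01 to -0.08. Spearman coefficients follow the same pattern (-0.02 to -0.14 for d = 1, b = 0).

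**Cross-check with a second glucose model.** A single lognormal with mean 8.6 mmol/L and CV 36% puts 1.8% of readings below 3.9. It gives r = -0.03, or +0.11 with b = 0.10. At CV 45% (5.2% low) and b = 0, r is -0.07.

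**Precision of the contrast.** The last column of the table shows that the contrast aims at the right quantity. It does not show precision in this trial, because clustering within patients was not modelled. By normal approximation, 80% power at two-sided 0.05 needs a paired difference of (1.96 + 0.84) / sqrt(20) = 0.63 SD of the within-patient differences. If only 13 patients contribute (65% of 20, borrowing the Background's figure), it needs 2.80 / sqrt(13) = 0.78. That SD is not the epoch SD used for d, so the two scales cannot be compared directly.

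**The case against.** The best defence is that the plan may not intend a whole-range coefficient at all. Statistical Analysis names no correlation coefficient and lists only comparison tests, one of them by glucose level. Correlation is also used loosely elsewhere: objective 2 correlates a state with ECG changes, and Data Analysis correlates ST shifts with symptoms. This stands in part. The whole-range reading is an inference from the word prevailing, and an analyst could comply by comparing levels. But one could equally comply by computing a single coefficient, and nothing says which result decides if the two disagree. A reader might infer that the plan has no comparison by glucose level for these outcomes; its statistical section does not support that.

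A reader might also infer that the correlation will have the wrong sign. The documents do not support this. A pure threshold effect only shrinks r; reversal needs an added effect of high glucose in the same direction. Separating hyperglycemia for heart rate variability allows for such an effect but is no evidence of one.

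A small r is not the same as a missed effect. If all 34,560 epochs were treated as independent, r = -0.02 would give z of about 0.02 x sqrt(34,560) = 3.7. That independence is not credible with 20 patients, and a significant coefficient of that size would still not say how large the hypoglycemia effect is.

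Scarce low readings also weaken the proposed contrast; that stands. So does the point that this is a feasibility pilot, where descriptive correlation is tolerable. It remains a reason to keep the correlation as description, not as the main answer to objective 2.

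**Conclusion.** The concern holds for arrhythmia measures, P wave measures and T wave alternans, as a mismatch between the question and the one outcome-specific analysis stated. It does not extend to heart rate variability, which is assessed by state. If 1% to 10% of epochs are low, a whole-range correlation turns a true 1 SD hypoglycemia effect into about r = -0.02 to -0.16, small but with the right sign. Zero or reversal is conditional: it needs a same-direction rise of roughly 0.01 to 0.11 SD per mmol/L above 10, depending on the share of low readings. The size rests on the assumed glucose distribution, cut-offs and low share, none of which the documents give, and on epoch-level simulation without clustering. The change is worth making before analysis; the point does not threaten the conduct of the study.

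**What to change.** For these outcomes, state in Data Analysis that the main analysis is the within-patient contrast of hypoglycemia with euglycemia, using the same three states as for heart rate variability. Fix the cut-offs in advance, for example below 3.9 and above 10 mmol/L. These are assumed values for analysis only, not a clinical definition.

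Fit a mixed model with patient as random effect, or apply the repeated-measures methods already listed in Statistical Analysis to glucose state, and name the outcomes that each method covers. Report the contrast with its 95% confidence interval and the number of patients and epochs that contribute low readings. Keep the whole-range correlation as descriptive.

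The cost is a few sentences of plan text and a little more analysis on the same data. The downside is precision: if few of the 20 patients have low readings, the interval will be wide, and the report should say so.

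### Bazett is the plan's only heart-rate correction of QT, so a QTc difference between glucose states could not be separated from a difference in heart rate

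*Combined protocol and SAP*

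**What the plan says.** The Data Analysis section gives one rule for correcting QT: "QTc will be calculated using Bazett's formula". No second formula, QT-RR model or heart-rate covariate for QTc appears there or under Statistical Analysis. The latter plans the "paired t test or the Wilcoxon signed rank test", and repeated-measures ANOVA or Friedman tests, all unadjusted.

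Heart rate is not ignored. Arrhythmia analysis is to be correlated with blood sugar, and "This will include standard diagnostic evaluation including mean, median and range of heart rate". ST shifts "will be correlated with metrics of heart rate variability, absolute heart rate and symptoms". The QT variability algorithm is one "which computed mean QT, QT variance, mean heart rate, and heart rate variance". Under Design, Specification of Endpoints, and Procedures, "The heart rate and QT interval will be measured at baseline and the end of each interval from the digitized ECG".

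No sentence says outright that QTc is compared between glucose states. I infer it from the repeated QT measurement, from the paired and repeated-measures tests, and from the general statement that "The results from the glucose sensor and the CardioSTAT monitor will be correlated and compared to each other".

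**The concern.** The same Design section says that "Hypoglycemia is likely to induce autonomic responses captured on the CardioSTAT". Such a response may change heart rate in exactly the state of interest. If it does, and Bazett's exponent does not fit these patients, QTc moves between states for a reason unrelated to repolarization. Pairing does not help, because the error lies inside each patient's own difference.

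Reporting heart rate would show that it moved, but not how much of a QTc difference comes from the correction. Objective 3 uses these data to design a later study, so a correction artefact could be carried forward as a signal, or a real effect could be masked.

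**Working it through.** **Inputs from the documents.** Bazett correction; 20 patients; two-sided significance level 0.05; paired test. The documents give no QTc effect, standard deviation, heart-rate change or QT-RR exponent, so there is no figure of the plan's own to reproduce.

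**Assumed inputs.** QT of 400 ms at 60 bpm; exponent b from 1/3 to 0.55; SD of paired QTc differences 15 to 25 ms; 10 to 20 patients with both states (20 is the best case).

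**Step 1: the shift.** Let QT = k × RR^b, with RR = 60/heart rate in seconds and k unchanged by glucose. Then Bazett QTc = QT/RR^0.5 = k × RR^(b − 0.5), and the false shift is k × [RR2^(b − 0.5) − RR1^(b − 0.5)]. It is zero only if b = 0.5 or RR1 = RR2.

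Example, 65 to 80 bpm at b = 1/3: RR falls from 60/65 = 0.923 to 60/80 = 0.75. QTc goes from 400 × 0.923^(−1/6) = 405.4 to 400 × 0.75^(−1/6) = 419.6, a shift of +14.3 ms before rounding.

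| Heart rate (bpm) | b = 1/3 | 0.40 | 0.45 | 0.50 | 0.55 |
|---|---|---|---|---|---|
| 70 to 75 | +4.7 | +2.8 | +1.4 | 0 | −1.4 |
| 65 to 80 | +14.3 | +8.5 | +4.2 | 0 | −4.1 |
| 70 to 65 | −5.0 | −3.0 | −1.5 | 0 | +1.5 |

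Values are in ms and scale with k: at 420 ms the +14.3 becomes 14.3 × 420/400 = +15.0.

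**Step 2: chance of p < 0.05 with no repolarization change.** Noncentral t with n − 1 degrees of freedom and noncentrality (shift/SD) × √n. For +14.3 ms, this is 14.3/25 × √10 = 1.81 at the low end and 14.3/15 × √20 = 4.26 at the high end.

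| Heart rate (bpm) | b = 1/3 | 0.40 | 0.50 | 0.55 |
|---|---|---|---|---|
| 70 to 75 | 8% to 27% | 6% to 12.5% | 5% | 5.3% to 6.7% |
| 65 to 80 | 37% to 98% | 16% to 67% | 5% | 7.5% to 21% |

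**Step 3: does another fixed exponent solve it?** No. Replace 0.5 by 1/3 (Fridericia) in the formula. For 65 to 80 bpm the shift is 0 at b = 1/3, −5.5 ms at 0.40, −13.4 ms at 0.50 and −17.3 ms at 0.55. Between 1/3 and 0.5 the two formulas err in opposite directions, so together they bracket the truth. Outside that range they err in the same direction.

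**Step 4: does a slope estimated from the data solve it?** Only with good data. In a simulation of 20 patients, +15 bpm and no QT effect, each patient had 300 euglycemic and 12 hypoglycemic epochs and a within-patient heart-rate SD of 8 bpm. The third row subtracts a pooled within-patient slope of log QT on log RR and then applies the paired test.

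| False rejection | b = 1/3 | 0.40 | 0.50 | 0.55 |
|---|---|---|---|---|
| Bazett | 77.8% | 37.0% | 5.5% | 13.4% |
| Fridericia | 5.0% | 19.4% | 75.0% | 92.5% |
| Pooled-slope adjustment | 4.8% | 5.0% | 5.4% | 4.2% |

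Separately coded simulation agreed closely, except for Bazett at 0.55 (9.4%).

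Poorer data change this. At b = 0.50, the pooled-slope test rejects about 38% with two measurements per state and a heart-rate SD of 2.5 bpm. With dense epochs but a 4 bpm error in epoch heart rate, it rejects about 36%. Bazett stays near 5% in both cases. The first failure arises because the paired test treats an estimated slope as known, the second because error in heart rate flattens the slope.

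**The case against.** **The premise is inferred twice.** The plan ties heart rate variability, arrhythmia measures, P wave measures and T wave alternans to glucose, but of QTc it says only that it will be calculated. A heart-rate difference is also an inference. Both objections stand, so the point is conditional on them.

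**Much is already in hand.** Heart rate will be correlated with blood sugar, QT and heart rate are both recorded, and T wave alternans, Tpeak-Tend and the QT variability index are planned too. This is a feasibility pilot with no ranked endpoints, and a different correction can be applied later. That limits the stakes. It does not remove the benefit of fixing the method before the results are seen.

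**The data may not support a model-based correction.** The sentence on QT variability refers to a baseline measurement, and the other QT schedule is baseline plus the end of each interval. Whether QT is measured densely in every glucose state is left open. This stands and decides the form of the fix. A reader might infer that a data-derived slope should replace Bazett as the main analysis, but the documents do not show that the data would support it.

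**Conclusion.** The point holds as a limit on interpretation. Bazett is the only correction, and nothing else in the plan adjusts QTc for heart rate. If QTc is compared between glucose states and heart rate differs between them, part or all of a QTc difference may come from the correction. Over the assumed ranges the false shift runs from −5.0 to +14.3 ms, and false rejection runs from the nominal 5% to 98%. At exponent 0.50 there is no bias.

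A reader might go further and infer that Bazett will falsely show QT prolongation in hypoglycemia here. The documents do not support that: they give neither the heart-rate change nor the exponent, and either sign is possible. Nor can it be said that the plan overlooks heart rate, which it measures and relates to glucose. What is missing is its use in reading QTc. This is a cheap improvement to consider, not a flaw that undermines the study.

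**What to change.** In the Data Analysis section, keep the Bazett sentence and add:

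> For any comparison of QTc between glucose states, mean heart rate in each state is reported beside QTc. The comparison is repeated with Fridericia QTc. Where per-epoch QT and heart rate are available in the compared states, it is also repeated with QT adjusted for RR by a within-patient model, for example a mixed model of log QT on log RR and glucose state with random patient and patient-by-state effects. A QTc difference is attributed to hypoglycemia only if its direction and approximate size hold across these analyses. Otherwise it is reported as not separable from heart rate.

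A mixed model covers two or three states and carries the uncertainty of the slope into the standard error. The patient-by-state effect prevents repeated epochs from counting as independent evidence. The section should also state whether QT and heart rate are measured per epoch in every glucose state, since the model depends on it.

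**Cost.** A few sentences and some extra analysis, with no new patients, visits or devices. The QTc conclusion becomes more cautious: a real effect may be reported as not separable when Fridericia is itself biased. Agreement of the two formulas is not proof if the exponent lies outside 1/3 to 0.5. The model result is unreliable when epochs are few, heart rate varies little within a state, or epoch heart rate is measured with error. It also assumes the same slope in every state. It should therefore stay a sensitivity analysis.
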